14.3. Analysis Populations

Safety Population:

All subjects who were administered any test article excluding subjects who drop out prior to administering any test article. At least one observation should be recorded.

Per-Protocol Population:

All subjects who have successfully completed all visits and did not substantially deviate from the protocol as determined by the trial cohort review committee prior to database hard lock (Per-Protocol Population). Justification of excluding subjects with protocol deviations in the Per-Protocol Population set will be documented in a memo to file.

Intent-to-Treat (ITT) Population:

All randomized subjects regardless of actual treatment and subsequent withdrawal from study or deviation from protocol. At least one observation should be recorded.

14.4. Level of Statistical Significance

All planned analysis for this study will be conducted with an overall type I error rate of 5%. Type I error will be controlled for multiplicity across interim analysis and final analysis.

14.5. Primary Analysis

Non-Invasive Break-Up Time / Non-Invasive Keratography Break-Up Time (in seconds)

Non-invasive tear break-up time among habitual contact lens wearers (the interventional arm) will be analyzed using a linear mixed model to compare between Test lens and Spectacles. The model will include lens type (Test lens/Spectacles), sequence of lens wear, period, subject group, and subject group by lens type interaction as fixed effects, and site and subject as random effects. Other baseline characteristics known of importance such as age and gender will be included as fixed covariates when appropriate. The covariance structure for the residual errors across different periods from the same subject and eye (R-side) will be selected based on the finite sample corrected Akaike's Information Criterion (Keselman et al. 1998). Two covariate structures will be considered: Homogenous Compound Symmetry (CS) and Unstructured covariance structure (UN). The homogeneity of the covariance structure across subject groups will be evaluated using a log-likelihood ratio test.

The null and alternative hypotheses for testing significant difference between Test lens and Spectacles among habitual lens users with respect to NIBUT/NIKBUT are presented below:

$$\begin{aligned} H_0: \mu_T - \mu_S &= 0 \\ H_a: \mu_T - \mu_S &\neq 0, \end{aligned}$$

where $\mu_T - \mu_S$ is the population mean difference (Test - Spectacles) in NIBUT/NIKBUT at 1-week follow-up.

Comparison on NIBUT/NIKBUT between Test lens and Spectacles will be carried out using a two-sided 95% confidence interval (CI) constructed of least-square means (LSM) difference from the linear mixed model (Test - Spectacles). A statistically significant difference in NIBUT/NIKBUT between Test lens and Spectacles will be concluded if the upper confidence limit of the 95% CI is below zero or the lower limit is above zero.

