2.3. Hypotheses

This is a pilot study and all the hypotheses are exploratory in nature.

Primary Hypotheses

There will be no difference between Test lens and Spectacles with respect to non-invasive break up time/ non-invasive keratography break up time among habitual contact lens wearers (the interventional arm) at 1-Week follow-up.

Secondary Hypotheses

There will be no secondary hypotheses. The following will be estimated for Test lens and Spectacles among habitual contact lens wearers at 1-Week follow-up:

- Total scores of Meibomian gland expressibility
- Average grades of conjunctival staining
- Proportions of eyes with clinically significant (Grade 3 or 4 of overall classification) lid wiper epitheliopathy

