5. TEST ARTICLE ALLOCATION AND MASKING

5.1. Test Article Allocation

Dispensed contact lenses will be worn in a bilateral fashion. Randomization is applicable in this study only in the interventional arm. Study lens and Spectacle will be worn in a bilateral

and random fashion for a period of 1 week each among subjects in the interventional arm. Subjects will be randomly assigned to one of two sequences (Spectacle /ACUVUE OASYS 1-Day or ACUVUE OASYS 1-Day /Spectacle). Groups based on the Classification questionnaire will be used as strata in the randomization, with a 1: 1 ratio for Group 1 (high use and symptomatic) and Group 2 (low use and/or asymptomatic) subjects.

The test article assignment of subjects must be performed at the Initial Visit. The following must have occurred prior to test article assignment:

- Informed consent has been obtained
- Subject meets all the applicable inclusion/exclusion criteria
- Subject history and baseline information has been collected

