| 2.4. | Subject Reported Ocular Symptoms | Subjects will respond to a verbal open-ended symptoms questionnaire. | |
| 2.5. | Follow-Up Spectacle Questionnaires (if applicable): DEQ-5, MRD, and Digital Device | The subject will respond to the Follow-Up Questionnaire. | |
| 2.6. | Follow-Up Contact lens Questionnaires (if applicable): CLDEQ-8, MRD, and Digital Device | The subject will respond to the Follow-Up Questionnaire. | |
| 2.7. | Visual Acuity | Perform monocular distance and near ETDRS LogMAR visual acuity test, OD & OS | |
| 2.8. | Subjective Lens Fit | Evaluate overall lens fit acceptance | |

| Visit 2: Treatment 1 Follow-Up 1 | | |
|----------------------------------|--|--|
| Step | Procedure | Details |
| | Assessment (if applicable) | 
(acceptable or unacceptable) based on centration, movement and other fitting characteristics.
 
An unacceptable fit is deemed by one of the following criteria:
 
 • limbal exposure at primary gaze or with extreme eye movement • edge lift • excessive movement in primary and up gaze • insufficient movement in all three of the following conditions: primary gaze, up gaze, and Josephson push up 
Note: if lens fit is unacceptable subject will be discontinued from the study.
 |
| 2.9. | Wettability Characteristics (if applicable) | Record the white light lens wettability of both lenses. |
| 2.10. | Surface Debris & Deposits (if applicable) | Record any front and back surface lens debris & deposits. |
| 2.11. | Tear film stability (Pre-Lens or Pre-Corneal as applicable) | Record the first tear film stability (NIBUT/NIKBUT), OD & OS. Record three measurements. |
| 2.12. | Blink patterns (as site applicable) | Record the Blink Patterns, OD & OS |
| 2.13. | Pre-corneal or Pre-lens (as applicable) tear film lipid layer thickness as available by site | Record the tear film lipid layer thickness, OD & OS |
| 2.14. | Lens Removal and Storage (if applicable) | 
The lenses will be removed by the subject. VRC site only, both lenses will be stored dry in a labeled glass vial and frozen, using study specific labels.
 
Otherwise, lenses will be discarded.
 |
| 2.15. | Slit Lamp Biomicroscopy | FDA Slit Lamp Classification Scale will be used to grade the findings and determine eligibility. |

| Visit 2: Treatment 1 Follow-Up 1 | | | |
|----------------------------------|---|---|---|
| Step | Procedure | Details | |

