14.2. Sample Size Justification

The plan is to enroll 70 eligible subjects with a minimum target of 60 subjects to complete the study. Of the total 60 subjects, 20 subjects will be habitual spectacle users (the observational arm) and 40 subjects will be habitual contact lens users (the interventional arm). The sample size was chosen by the project team, given that this study is to gain initial insights of the performance of Test lens compared to Spectacles among different users (habitual lens users and habitual spectacle users). Therefore, the sample size was not based on any empirical sample size calculation.

The power was calculated for testing the primary hypothesis based on the selected sample size of 40 subject in the intervention arm using a 2×2 cross-over design. The calculation was performed with a 2-sided type I error of 0.05 assuming the true difference of 2 (seconds) in NIBUT between Test lens and Spectacles using a linear mixed model-based power analysis method (Stroup, 1999; 2002). Historical data from [REDACTED] were used to obtain the overall variance of NIBUT. The overall variance of NIBUT was about 34 based on the historical data. The intra-class correlation between measurements obtained from the same subject and eye across periods was assumed to be $ICC_{eye(subj)} = 0.5$, and the intra-class correlation between measurements obtained from the same subject across eyes and periods was assumed to be $ICC_{subj} = 0.3$. The SAS procedure PROC GLIMMIX (SAS software Version 9.4) was used to perform the calculation.

Based on the calculation, if the true difference is expected to be 2 seconds in NIBUT, the sample size of 40 subjects (80 eyes) using a 2×2 crossover design has a power of 86% to test for a significant difference between Test lens and Spectacles with a two-sided type I error of 0.05.

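### The primary model and the 86% power treat a subject's two eyes as giving independent Test − Spectacles differences; if fellow eyes share period-specific variation, the 95% CI is too narrow

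*Combined protocol and SAP*

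**What the plan says.** Only the interventional arm is randomised, and sequence is assigned by subject (Section 5.1). In the same section, "Dispensed contact lenses will be worn in a bilateral fashion". At each follow-up visit both eyes are tested together: "Record the first tear film stability (NIBUT/NIKBUT), OD & OS. Record three measurements" (Section 7.2, steps 2.11 and 4.11).

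Section 14.5 specifies a linear mixed model with lens type, sequence, period, subject group and "subject group by lens type interaction as fixed effects, and site and subject as random effects". The remaining covariance is described as "The covariance structure for the residual errors across different periods from the same subject and eye (R-side"), with compound symmetry (CS) or unstructured (UN) chosen by corrected AIC. Significance is declared when the 95% CI for the least-squares mean difference excludes zero.

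Section 14.2 assumes a NIBUT variance of about 34, a true difference of 2 s and a correlation of 0.5 for the same eye across periods. It then says "the intra-class correlation between measurements obtained from the same subject across eyes and periods was assumed to be" 0.3. No separate value is given for fellow eyes within the same period. It concludes that "the sample size of 40 subjects (80 eyes) using a 2×2 crossover design has a power of 86"%.

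Section 14.4 states: "All planned analysis for this study will be conducted with an overall type I error rate of 5"%. Section 2.3 states: "This is a pilot study and all the hypotheses are exploratory in nature".

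**The concern.** The unit of randomisation is the subject, and in each period both eyes receive the same treatment. Anything that moves both eyes together at one visit and differs at the next (the participant's tolerance of holding the eye open, the examiner, conditions on the day) is therefore confounded with the lens effect within that subject. It averages out only over 40 subjects, not 80 eyes.

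The planned model has nowhere to put this variation. The random subject and site effects are constant over periods and drop out of every Test − Spectacles difference. CS and UN both describe two periods within one eye, so choosing between them cannot create a link between right and left eyes within a period. Because each subject has one treatment per period, the missing term can be called subject-by-period or subject-by-lens.

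At stake are the coverage of the interval that Section 14.5 uses as its decision rule, the 5% rate promised in Section 14.4, and the 86% power in Section 14.2.

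**Working it through.** **Inputs (Section 14.2).** Variance 34; same-eye correlation across periods 0.5; fellow-eye correlation across periods 0.3; 40 subjects (80 eyes); difference 2 s; two-sided 5%.

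**Assumed, not in the documents.** The same-period fellow-eye correlation *r*. The range starts at 0.3, the value implied by the planned model. Its ceiling is 0.8, where the two eye differences are perfectly correlated. The algebra takes one value per eye and period, complete balanced data, and no site or covariate adjustment.

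**Step 1: reproduce the plan's power.**
- Var(one eye's difference) = 2 × 34 × (1 − 0.5) = 34.
- With 80 uncorrelated differences, SE = √(34/80) = 0.652 s, and 2/0.652 = 3.07.
- Power is 85.8% (t, 77 df), 86.1% (t, 118 df) or 86.6% (normal). The stated 86% is reproduced.

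**Step 2: what that implies about fellow eyes.**
- Cov(right difference, left difference) = 34 × (*r* − 0.3 − 0.3 + *r*) = 2 × 34 × (*r* − 0.3).
- Dividing by 34, the correlation of the two differences is ρ = 2(*r* − 0.3).
- This is zero only at *r* = 0.3. The planned model forces that, because its only between-eye covariance is the subject variance, which is the same within and across periods.

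**Step 3: true standard error.** SE = √(34(1 + ρ)/80).

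**Step 4: what the planned model estimates.** With balanced data its residual variance pools two strata:
- the mean of the two eye differences: 40 subjects less 3 parameters (lens, period, group-by-lens) = 37 df, expectation proportional to 34(1 + ρ);
- the right − left contrast: 40 df, expectation proportional to 34(1 − ρ).

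The pooled expectation is 34 × [37(1 + ρ) + 40(1 − ρ)]/77 = 34(1 − 3ρ/77), so the planned SE stays near 0.65 s whatever ρ is. A valid test uses the 37-df stratum alone.

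**Step 5: results.** Type I error is from 2,000,000 draws of the two strata per value. Power is from the noncentral t with 37 df. CI half-widths use t with 77 df (planned) and 37 df (valid).

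| *r* (assumed) | 0.3 | 0.4 | 0.5 | 0.6 | 0.7 |
|---|---|---|---|---|---|
| ρ | 0 | 0.2 | 0.4 | 0.6 | 0.8 |
| True SE (s) | 0.652 | 0.714 | 0.771 | 0.825 | 0.875 |
| Planned CI half-width (s) | 1.30 | 1.29 | 1.29 | 1.28 | 1.28 |
| Valid CI half-width (s) | 1.32 | 1.45 | 1.56 | 1.67 | 1.77 |
| Type I error, planned test | 5.0% | 7.4% | 10.0% | 12.6% | 15.1% |
| Coverage, planned CI | 95.0% | 92.6% | 90.0% | 87.4% | 84.9% |
| Power of valid test, 2 s | 85% | 78% | 71% | 66% | 61% |

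**Step 6: does CS or UN matter?** The planned model (without site) was fitted by REML to 600 simulated trials per setting. Type I error was 5.0–5.3% at *r* = 0.3, 9.7–9.8% at 0.5 and 15.7–16.2% at 0.7. The rates were similar under CS and UN.

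**The case against.** The harm depends on a number that the documents do not give. Section 14.2 can be read as a deliberate assumption that 0.3 applies to every pair of fellow-eye readings, and under that assumption the planned test holds its level. If *r* were below 0.3, the CI would be too wide instead. This stands: the size of the problem is not established, only its direction when *r* exceeds 0.3.

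The upper end of the range is also demanding. Given 0.3 and 0.5, the share of variance that is specific to one eye at one visit is 0.8 − *r*. That is 20% at *r* = 0.6 (SD √6.8 = 2.6 s) and 10% at 0.7 (SD √3.4 = 1.8 s). The Medmont work aid has an observer time each eye by stopwatch, and that adds eye-specific noise. This too stands. The 0.3 to 0.5 columns deserve most weight, and 0.4 is the only value shown strictly between the plan's two correlations.

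The study is a pilot, and Section 14.2 says the sample size was the project team's choice, so 86% did not determine N. That lowers the stakes but does not remove the 5% rate and the CI decision rule that Sections 14.4 and 14.5 adopt.

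Finally, the figures are tidier than the data will be. Three readings per eye are recorded without a stated rule for combining them, and step 4.11 is done only where a site has the equipment. This affects precision, not the missing term.

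On the other side, a same-period excess is plausible from the design: bilateral wear, one visit, and an endpoint (Section 2.2) that can end when the participant has to blink.

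**Conclusion.** The concern holds, conditionally. It is certain from the text that neither the model nor the power inputs allow fellow eyes to share period-specific variation, and that 86% corresponds to 80 uncorrelated eye differences. Nothing elsewhere in Section 14 compensates: there is no robust standard error, two-eye averaging or subject-by-period term.

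The consequence rests on the assumed *r*. There is no error at 0.3. At 0.4 the true type I error is 7.4% and valid power 78%; at 0.5 they are 10.0%, double the nominal rate, and 71%. Larger values are possible but less likely. The point should be fixed before database lock. It concerns the validity of the interval and the accuracy of the power statement, not the choice of sample size.

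**What to change.** **Section 14.5.** Add a random subject-by-period effect to the listed random effects and specify Kenward-Roger degrees of freedom. With complete data, analysing the mean of the two eyes per subject and period is an acceptable alternative. State whether the new variance component may go negative. If it is bounded at zero and estimated there, the fit reverts to the planned model.

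**Section 14.2.** State that 86% assumes uncorrelated fellow-eye differences, and give power over a range of ρ starting at 0, as in the table.

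**Cost.** One line of wording and one RANDOM statement; no extra subjects are needed for a valid analysis. If ρ = 0, power falls from 85.8% to 84.8% (two-eye mean, or component left unbounded). If the component is bounded, it is estimated as zero in about half of trials, power is about 83.7% and type I error about 4.3%.

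If ρ > 0, the power reported for 40 completers will be lower than 86%. Keeping 86% would need about (1.960 + 1.080)² × 34(1 + ρ)/(2 × 2²) = 39.3(1 + ρ) completers by the normal approximation: 48, 55, 63 and 71 at *r* = 0.4, 0.5, 0.6 and 0.7. For a pilot, reporting the lower power is enough.

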14.6. Secondary Analysis

Meibomian Gland Expressibility

The average of Meibomian gland expressibility Total scores will be calculated and compared between Test lens and Spectacles among habitual contact lens users (the interventional arm) at 1-week follow-up.

Conjunctival Staining

The average grades of conjunctival staining will be calculated and compared between Test lens and Spectacles among habitual contact lens users (the interventional arm) at 1-week follow-up.

Lid Wiper Epitheliopathy

The proportion of eyes with clinically significant (Grade 3 or 4 for overall classification) lid wiper epitheliopathy will be calculated and compared between Test lens and Spectacles among habitual contact lens users (the interventional arm) at 1-week follow-up.

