2.2. Endpoints

Primary Endpoint(s)

Non-invasive break up time (NIBUT)/ non-invasive keratography break up time (NIKBUT) time in seconds

NIBUT/NIKBUT is measured as the time interval in seconds after the final blink to the first appearance of distortion in the reflected rings; or to the time that the participant has to blink due to discomfort.

Secondary Endpoint(s)

Meibomian Gland Expressibility (Appendix I)

Meibomian gland expressibility is assessed in three regions of the lower eyelid: temporal, central, and nasal. Approximately five glands are expressed per region and evaluated using a four-grade scale: 0 = No Secretion, 1 = Inspissated, 2 = Colored/Cloudy Liquid, and 3 = Clear Liquid Oil. The total score is calculated as the sum of all grades across the three regions and ranges from 0 to 45.

Conjunctival Staining

Conjunctival staining is graded and recorded by quadrant (Superior, Inferior, Nasal, and Temporal) using the following grading scale: Grade 0 = None, Grade 1 = Trace, Grade 2 = Mild, Grade 3 = Moderate, and Grade 4 = Severe. Average grade can be calculated based on grades of the four quadrants.

Lid Wiper Epitheliopathy (Appendix H)

Horizontal lid margin staining and sagittal lid margin staining are graded for each eyelid separately. The horizontal and sagittal grades are then averaged for each eyelid to obtain the upper lid average grade and lower lid average grade. The final grade is the average of the upper and lower lid average grades. Subjects can be classified according to their final grades for each eye. The classification is defined as follows: “None” for final grades of 0, “Mild” for final grades between 0.25 and 1.00, “Moderate” for final grades between 1.25 and 2.00, and “Severe” for final graded between 2.25 and 3.00.

Other Exploratory Endpoint(s)

Subjective Comfort Assessed by (0-100) Numeric Scale

Subjective comfort will be assessed using a numeric scale which ranges from 0 to 100, where 100 is defined as “Best comfort imaginable” and 0 as “Worst comfort imaginable”.

Dry Eye Symptoms Measured by CLDEQ-8 and/or DEQ-5

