- b. The superior bulbar conjunctiva if conjunctival staining is not going to be assessed as part of the protocol. If instilling the dye in this location take care that the upper lid wiper is not touched during instillation.
5. With a new dye strip, immediately repeat steps 1-4 for the same eye to complete a second strip dose for the first dye instillation.
6. Perform the next step after a wait time of 1 minute.
7. With two new dye strips, perform a second instillation of lissamine green dye by repeating steps 1 through 5. Note that four dye strips have been used for one eye.
8. Perform the next step after a wait time of 3 minutes.
9. Evert the lower eyelid of one eye with care to avoid contact with the lid wiper.
10. Evaluate the lower lid margin under white light, 10X magnification recommended.
11. Examine the entire horizontal length of the lid wiper from the punctum to the lateral canthus. Preferred method of grading of length in mm is via slit lamp reticle, but slit beam length may also be used if needed. Grade the horizontal length of staining observed to the nearest mm as shown in Table 1 on a scale of 0 to 3. Note that if there are separate areas of staining along the entire horizontal length of the lid wiper, sum the areas together to determine the grade. Document the horizontal length staining grade.

Table 1: Horizontal Length of Lid Wiper Grading Scale

| GRADE | HORIZONTAL LENGTH OF STAINING |
|-------|-------------------------------|
| 0 | < 2 mm |
| 1 | 2 ≥ to < 4.5 mm |
| 2 | 4.5 ≤ to < 9.5 mm |
| 3 | ≥ 9.5 mm |

12. Examine the entire sagittal height (width) of the lid wiper from proximal to the line of Marx to the subtarsal fold. Grade the sagittal height of staining observed based on the percentage of staining over the width of the lid wiper, as shown in Table 2 on a scale of 0 to 3. Note that if there is a range of staining along the width of the lid wiper, estimate the average width to determine the grade. Document the sagittal height staining grade.

Table 2: Sagittal Height (Width) of Lid Wiper Grading Scale

| GRADE | SAGITTAL HEIGHT (WIDTH) OF STAINING |
|-------|-------------------------------------|
| 0 | < 25% |
| 1 | 25% to < 50% |
| 2 | 50% to < 75% |
| 3 | ≥ 75% |

13. Repeat steps 9 through 12 on the upper lid.

14. If eyelid photography is indicated, follow the steps in Appendix A. Repeat all of the above steps for the fellow eye.

Grading:

| | OD | | OS | |

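### The lid wiper epitheliopathy proportion counts Grade 3 or 4, but its four classes are unnumbered and no Grade 4 exists, so it is unclear whether Moderate eyes count

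*Combined protocol and SAP*

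**What the plan says.** Section 2.3 lists among the quantities to be estimated "Proportions of eyes with clinically significant (Grade 3 or 4 of overall classification) lid wiper epitheliopathy". Section 14.6 repeats the rule as "The proportion of eyes with clinically significant (Grade 3 or 4 for overall classification) lid wiper epitheliopathy" and says that the proportion will be compared between Test lens and Spectacles in the interventional arm at one week.

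The classification is defined in Section 2.2. Horizontal and sagittal grades are averaged within each lid, and the two lid averages are averaged to give the eye's final grade. Then "Subjects can be classified according to their final grades for each eye": None is a final grade of 0, Mild is 0.25 to 1.00, Moderate is "for final grades between 1.25 and 2.00" and Severe is "for final graded between 2.25 and 3.00". These classes have names and ranges but no numbers.

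The component grades come from Appendix H. Step 11 reads "Grade the horizontal length of staining observed to the nearest mm as shown in Table 1 on a scale of 0 to 3", and step 12 uses the same 0 to 3 range for sagittal height. The recording note there says that eight grades are recorded per evaluation and that grades are not averaged.

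Section 2.2 does define a Grade 4, but for conjunctival staining: "Grade 3 = Moderate, and Grade 4 = Severe".

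**The concern.** The threshold does not fit the scale to which it is applied. Neither a component grade nor a final grade can reach 4, and the overall classes carry no numbers, so a programmer has to supply a numbering. The two natural choices give different endpoints.

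LWE is one of three secondary endpoints, and the Test lens versus Spectacles comparison on it is a secondary objective. Section 14.7 extends the comparison with habitual spectacle wearers to all endpoints, so the ambiguity carries over there. Section 5.2 states that subjects and investigators know the assignment. A cut-off left open until the data are in could therefore be settled with results in view. Section 14.10 requires changes of method to be documented, but choosing between two readings of an undefined threshold need not register as a change.

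**Working it through.** The plan gives no figure for the LWE proportion, so there is none to reproduce. The check is whether the stated rule can be applied to the stated scale, and how far the readings diverge.

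**Inputs.** Four component grades per eye (upper and lower lid, horizontal and sagittal), each 0 to 3 (Appendix H). Averaging rule and class ranges from Section 2.2. 40 completing subjects in the interventional arm, hence 80 eyes (Section 14.2).

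**Range of the scale.** Final grade = (sum of the four grades) / 4. The sum runs from 0 to 12, so the final grade runs from 0 to 3.00 in steps of 0.25. The four ranges in Section 2.2 cover every possible value without gap or overlap. The maximum is 3.00, so a final grade of 4 cannot occur.

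**Grade patterns in each class.** There are 4^4 = 256 combinations:

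| Class | Sum of grades | Final grade | Patterns |
|---|---|---|---|
| None | 0 | 0 | 1 |
| Mild | 1 to 4 | 0.25 to 1.00 | 4 + 10 + 20 + 31 = 65 |
| Moderate | 5 to 8 | 1.25 to 2.00 | 40 + 44 + 40 + 31 = 155 |
| Severe | 9 to 12 | 2.25 to 3.00 | 20 + 10 + 4 + 1 = 35 |

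The total is 1 + 65 + 155 + 35 = 256.

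**Readings of the rule.**

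| Reading | What counts | Patterns counted |
|---|---|---|
| Classes numbered 1 to 4 | Moderate or Severe, final grade ≥ 1.25 | 155 + 35 = 190 |
| Classes numbered 0 to 3 | Severe only, final grade ≥ 2.25; Grade 4 empty | 35 |
| Number read as the final grade itself | Final grade of exactly 3.00 | 1 |

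The third reading fits least well, because both sections refer to the overall classification and not to the final grade. The two class-based readings differ by 190 − 35 = 155 patterns, which are exactly the Moderate ones. These counts show which eyes would change status; they are not prevalences.

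**In eyes.** The documents give no LWE distribution. As an assumption, take a Moderate share of 10%, 20%, 30% or 40% under one correction. The number of eyes counted for that correction then differs between the two readings by 80 × share = 8, 16, 24 or 32.

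**In the comparison.** Write m for the Moderate share and s for the Severe share, with T for Test lens and S for Spectacles. The planned difference is (m_T + s_T) − (m_S + s_S) under the first reading and s_T − s_S under the second. They differ by m_T − m_S. The effect on the comparison is zero if the Moderate shares are equal. It is 30 percentage points if the shares sit at opposite ends of the assumed range (40% − 10%).

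**The case against.** The strongest reply is that the intent can be recovered. Both sections tie the rule to the overall classification. There is only one such classification for LWE, it has four ordered classes, and the third and fourth are Moderate and Severe. Severe-only makes the 4 meaningless in both places where it appears. The conjunctival scale also labels its Grades 3 and 4 Moderate and Severe. This makes Moderate-or-Severe the likelier reading, but it remains an inference. The LWE component grades, the meibomian scale and the conjunctival scale all start at 0, and numbering the LWE classes the same way gives Severe only. The conjunctival scale has five classes and belongs to a different endpoint.

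It can also be said that the pattern counts and the 8 to 32 eyes do not measure the effect on the result. That is right. Middle sums have the most combinations, so Moderate dominates the pattern count by construction; the eye counts rest on an assumed share; and the between-treatment difference may not move at all. The point rests on the undefined threshold, not on these figures.

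Finally, the stakes are limited. Section 2.3 calls the study a pilot and states "There will be no secondary hypotheses". Because the component grades are recorded, either cut-off can be derived later. This limits the weight of the point, but the reported proportion is the result for this endpoint and still needs a definition.

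The Appendix H note against averaging is not a real contradiction of Section 2.2. It sits beside the recording grid and reads as an instruction on what to record.

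**Conclusion.** The concern holds as stated and should be fixed. The rule in Sections 2.3 and 14.6 refers to a grade that the LWE scale does not have, and nothing maps its numbers to the four classes. The probable meaning (final grade 1.25 or more) and the zero-based reading (2.25 or more) give proportions that differ by the full share of Moderate eyes. That statement needs no assumption. The 8 to 32 eyes per correction assume a Moderate share of 10% to 40% of 80 eyes, and the effect on the Test lens minus Spectacles difference depends on how that share differs between the two. The consequence is confined to this one secondary endpoint. The primary NIBUT comparison and its power do not depend on it.

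**What to change.** In Sections 2.3 and 14.6, replace the grade numbers with the class names and the cut-off on the Section 2.2 final-grade scale: for example, eyes classed Moderate or Severe, final grade 1.25 or more, if the sponsor confirms that intent. Fix this before database lock. As a clarification, add one sentence to Appendix H saying that the eight grades are recorded unaveraged and are averaged at analysis as Section 2.2 describes.

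The cost is wording in three places. No new data, visits or procedures are needed, because all the component grades are already recorded.
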